3.2 Registration – Exclusion Criteria

3.21 Any of the following because this study involves an investigational agent whose genotoxic, mutagenic and teratogenic effects on the developing fetus and newborn are unknown:

- Pregnant women
- Nursing women
- Men or women of childbearing potential who are unwilling to employ adequate contraception

NOTE: Female subjects of childbearing potential should be willing to use 2 methods of birth control or be surgically sterile, or abstain from heterosexual activity for the course of the study through 120 days after the last dose of study medication (Reference Section 5.7.2). Subjects of childbearing potential are those who have not been surgically sterilized or have not been free from menses for > 1 year. Male subjects should agree to use an adequate method of contraception starting with the first dose of study therapy through 120 days after the last dose of study therapy. Abstain from heterosexual activity is also acceptable method of contraception for males.

- 3.22 Co-morbid systemic illnesses or other severe concurrent disease which, in the judgment of the investigator, would make the patient inappropriate for entry into this study or interfere significantly with the proper assessment of safety and toxicity of the prescribed regimens.
- 3.23 Known history of Human Immunodeficiency Virus (HIV) (HIV 1/2 antibodies).
- 3.24 Uncontrolled intercurrent illness including, but not limited to, ongoing or active infection, symptomatic congestive heart failure, unstable angina pectoris, cardiac arrhythmia, or psychiatric illness/social situations that would limit compliance with study requirements.
- 3.25 Receiving any other investigational agent which would be considered as a treatment for the primary neoplasm or used an investigational device ≤ 4 weeks from registration.
- 3.26 History of myocardial infarction ≤ 6 months, or congestive heart failure requiring use of ongoing maintenance therapy for life-threatening ventricular arrhythmias.
- 3.27 Known history of active TB (Bacillus Tuberculosis)
- 3.28 Hypersensitivity to pembrolizumab or any of its excipients.
- 3.29a Prior anti-cancer monoclonal antibody (mAb) ≤ 4 weeks prior to registration or who has not recovered (i.e., \leq Grade 1 or at baseline) from adverse events due to agents administered more than 4 weeks prior to registration

- 3.29b Prior chemotherapy, targeted small molecule therapy, or radiation therapy ≤ 2 weeks prior to registration or who has not recovered (i.e., \leq Grade 1 or at baseline) from adverse events due to a previously administered agent.

Note: Subjects with \leq Grade 2 neuropathy are an exception to this criterion and may qualify for the study.

Note: If subject received major surgery, they must have recovered adequately from the toxicity and/or complications from the intervention prior to starting therapy.

- 3.29c Known secondary malignancy that has progressed within the last 3 years or requires active treatment. Exceptions include basal cell carcinoma of the skin or squamous cell carcinoma of the skin that has undergone potentially curative therapy or in situ cervical cancer.
- 3.29d Known central nervous system (CNS) metastases and/or carcinomatous meningitis.
- 3.29e Active autoimmune disease that has required systemic treatment in the past 2 years (i.e. with use of disease modifying agents, corticosteroids or immunosuppressive drugs). Replacement therapy (eg., thyroxine, insulin, or physiologic corticosteroid replacement therapy for adrenal or pituitary insufficiency, etc.) is not considered a form of systemic treatment.
- 3.29f History of (non-infectious) pneumonitis that required steroids or current pneumonitis.
- 3.29g Active infection requiring systemic therapy.
- 3.29h History or current evidence of any condition, therapy, or laboratory abnormality that might confound the results of the trial, interfere with the subject's participation for the full duration of the trial, or is not in the best interest of the subject to participate, in the opinion of the treating investigator.
- 3.29i Known psychiatric or substance abuse disorders that would interfere with cooperation with the requirements of the trial.
- 3.29j Received prior therapy with an anti-PD-1, anti-PD-L1, or anti-PD-L2 agent.
- 3.29k Known active Hepatitis B (e.g., HBsAg reactive) or Hepatitis C (e.g., HCV RNA [qualitative] is detected).
- 3.29l Received a live vaccine ≤ 30 days prior to registration.

Note: Seasonal influenza vaccines for injection are generally inactivated flu vaccines and are allowed; however intranasal influenza vaccines (e.g., Flu-Mist®) are live attenuated vaccines, and are not allowed.

4.0 Test Schedule

Tests and Procedures	≤28 Days prior to Registration	Day 1 (+/-3 days) of each cycle	End of Treatment	Observation	
				Every 12 (+/- 2) weeks for months 24 thru 36 post registration	at progression
History and Physical Examination, wt, PS	X	X	X	X	X
Height	X				
Adverse Events Assessment	X	X	X	X	X
Pregnancy Test – Urine or Serum –HCG ¹		X ⁶			
CBC w/diff	X ²	X	X	X	X
Renal Profile: Sodium, Potassium, Chloride, Bicarbonate, Creatinine, Bun, Glucose	X ²	X	X	X	X
Albumin, bilirubin total and direct, alkaline phosphatase, total protein, AST, and ALT	X ²	X			
FT4 and TSH	X	X	X		
Disease Evaluation ³	X	X ⁴	X	X	X
Research Tissue Collection ^R		X ⁵			
Photograph of lesions	X	X	X	X	X

1. For women of childbearing potential only. Must be done ≤72 hours prior to registration.

2. ≤14 Days prior to Registration

3. Radiographic tumor imaging assessments must include CT scan, PET/CT, or MRI of the chest, abdomen, and pelvis. CT scan or MRI of the brain with contrast will only be performed if symptoms or signs of CNS metastasis are present. Use same imaging throughout the study.

4. At the completion of cycle 4 (approximately week 12) and then at completion of every 4th cycle (approximately every 12 weeks) thereafter (±7days) until PD.

5. Tissue specimens must be collected and submitted after registration but prior to the start of treatment, at completion of cycles 2 and 4 (approximately weeks 6 and 12).

6. For women of childbearing potential only. Must be done ≤ 72 hours prior to start of treatment. Must be repeated if pre-registration test is > 72 hours prior to the start of treatment.

R Research funded (see Section 19.0)

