8.0 Dosage Modification Based on Adverse Events

8.1 Dose-Modification Guidelines for Drug Related Adverse Events for Pembrolizumab

CTCAE System/Organ/Class (SOC)	ADVERSE EVENT	Hold Treatment for Grade	Timing for Restarting Treatment	Discontinue Subject
Gastrointestinal disorders	Diarrhea/Colitis	2-3	AE resolves to Grade 0-1	Toxicity does not resolve within 12 weeks of last dose or inability to reduce corticosteroid to 10mg or less of prednisone or equivalent per day within 12 weeks.
		4	Permanently discontinue	Permanently discontinue
Investigations	AST, ALT, or Blood bilirubin	2	AE resolves to Grade 0-1	AE does not resolve within 12 weeks of last dose
		3-4	Permanently discontinue (see exception below) ^a	Permanently discontinue
Metabolism and nutrition disorders	Glucose intolerance (Type 1 diabetes mellitus [if new onset] or Hyperglycemia)	Type 1 diabetes mellitus or 3-4	Hold pembrolizumab for new onset Type 1 diabetes mellitus or Grade 3-4 hyperglycemia associated with evidence of beta cell failure.	Resume pembrolizumab when patients are clinically and metabolically stable.
Endocrine disorders	Hypophysitis	2-3	AE resolves to Grade 0-1	AE does not resolve within 12 weeks of last dose or inability to reduce corticosteroid to 10mg or less of prednisone or equivalent per day within 12 weeks
		4	Permanently discontinue	Permanently discontinue
Endocrine disorders	Hyperthyroidism	3	AE resolves to Grade 0-1	AE does not resolve within 12 weeks of last dose or inability to reduce corticosteroid to 10 mg or less of prednisone or equivalent per day within 12 weeks.
		4	Permanently discontinue	Permanently discontinue

CTCAE System/Organ/Class (SOC)	ADVERSE EVENT	Hold Treatment for Grade	Timing for Restarting Treatment	Discontinue Subject
Endocrine disorders	Hypothyroidism	2-4	Therapy with pembrolizumab can be continued while treatment for the thyroid disorder is instituted	Therapy with pembrolizumab can be continued while treatment for the thyroid disorder is instituted.
General disorders and administration site conditions	Infusion reaction	3-4	Permanently discontinue	Permanently discontinue
Respiratory, thoracic and mediastinal disorders	Pneumonitis	2	AE resolves to Grade 0-1	AE does not resolve within 12 weeks of last dose or inability to reduce corticosteroid to 10mg or less of prednisone or equivalent per day within 12 weeks.
		3-4	Permanently discontinue	Permanently discontinue

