9.5 General patient monitoring and supportive care guidelines

9.51 Patients should be carefully monitored during the treatment phase and then followed appropriately. Decisions for retreatment or dose modifications/interruption should follow the guidelines in Sections 8.2.

9.52 Patients who have an ongoing study agent-related serious adverse event upon study completion or at discontinuation from the study will be contacted by the treating physician or his/her designee at least every 2 weeks until the event is resolved or determined to be irreversible.

- 9.6 Side effect management for **PEMBROLIZUMAB** toxicities- these are to be regarded as guidelines for managing toxicity that occurs with pembrolizumab therapy and should not replace clinical judgement (i.e. - patients with grade 1 rash may require systemic steroids).

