9.62 Rash

- 9.621 Grade 2- Initiate therapy with topical or systemic steroids at 0.5-1mg/kg/day of prednisone or equivalent.
- 9.622 Grade 3 or greater. Initiate systemic steroid therapy at 1-2 mg/kg/day of prednisone or equivalent.

- 9.63 Hyperthyroidism
 - 9.631 Grade 3- Initiate systemic steroid treatment at 1-2 mg/kg/day of prednisone or equivalent.
 - 9.632 Grade 4 - Initiate systemic steroid therapy at 1-2 mg/kg/day of prednisone or equivalent.
- 9.64 Immune-Mediated Hypophysitis
 - 9.641 Grade 2 and 3 – Initiate systemic steroid at 0.5-1mg/kg/day of prednisone or equivalent and physiologic replacement dose.
 - 9.642 Grade 4 – Initiate systemic steroid at 1-2 mg/kg/day of prednisone or equivalent and physiologic replacement dose.
- 9.65 Pneumonitis
 - 9.651 Grade 1- No change in treatment
 - 9.652 Grade 2- Initiate steroids at 0.5-1mg/kg/day of prednisone or equivalent.
 - 9.653 Grade 3 or greater- Consider hospitalization, and initiate systemic steroids
- 9.66 Liver Dysfunction (AST or ALT)
 - 9.661 $AST \text{ or } ALT \leq 3 \text{ ULN}$ - No change in treatment
 - 9.662 $AST \text{ or } ALT > 3 \text{ but } < 5 \text{ ULN}$ or Grade 2- Consider initiating systemic steroids at 0.5-1mg/kg/day of prednisone or equivalent.
 - 9.663 $AST \text{ or } ALT \geq \text{Grade 3}$ - Discontinue pembrolizumab. Initiate systemic steroid therapy.
- 9.67 Liver Dysfunction (Bilirubin)
 - 9.671 Grade 1- No change in treatment
 - 9.672 Grade 2- Consider initiating systemic steroids at 0.5-1mg/kg/day of prednisone or equivalent.
 - 9.673 Grade 3 or greater- Monitor levels until resolved to \leq Grade 1. Initiate therapy with steroids at 1-2 mg/kg/day of prednisone or equivalent.

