10.6 Required Routine Reporting

10.61 Baseline and Adverse Events Evaluations

Pretreatment symptoms/conditions to be graded at baseline and adverse events to be graded at each evaluation per CTCAE v4.0 grading **unless** otherwise stated in the table below:

System Organ Class (SOC)	Adverse event/Symptoms	Baseline	Each evaluation
Blood and lymphatic system disorders	Anemia	X	X
	Febrile Neutropenia		X
Cardiac Disorders	Myocardial infarction		X
Gastrointestinal disorders	Nausea	X	X
	Vomiting	X	X
	Abdominal pain	X	X
	Baseline # of stools	X	

	Diarrhea		X
General disorders and administration site conditions	Fatigue	X	X
	Fever		X
Immune system disorders	Allergic reaction		X
	Anaphylaxis		X
Investigations	Neutrophil count decreased		X
	Platelet count decreased		X
	White blood cell decreased		X
	Aspartate aminotransferase increased	X	X
	Alkaline phosphatase increased	X	X
	Blood bilirubin increased	X	X
Musculoskeletal and connective tissue disorders	Arthralgia	X	X
	Myalgia	X	X
Nervous system disorders	Peripheral sensory neuropathy	X	X

10.62 Submit via appropriate MCCC Case Report Forms (i.e., paper or electronic, as applicable) the following AEs experienced by a patient and not specified in Section 10.6:

10.621 Grade 2 AEs deemed *possibly, probably, or definitely* related to the study treatment or procedure.

10.622 Grade 3 and 4 AEs regardless of attribution to the study treatment or procedure.

10.623 Grade 5 AEs (Deaths)

10.6231 Any death within 30 days of the patient's last study treatment or procedure regardless of attribution to the study treatment or procedure.

10.6232 Any death more than 30 days after the patient's last study treatment or procedure that is felt to be at least possibly treatment related must also be submitted as a Grade 5 AE, with a CTCAE type and attribution assigned.

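### The liver panel is not scheduled at End of Treatment, so a new asymptomatic hepatic event after the final Day 1 draw could go unrecorded (cheap improvement, minor)

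*Combined protocol and SAP*

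**What the plan says.** Section 4.0 schedules "Albumin, bilirubin total and direct, alkaline phosphatase, total protein, AST, and ALT" within 14 days before registration and on Day 1 of each cycle. The End of Treatment cell and both Observation cells in that row are empty, and no footnote adds a panel.

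Section 10.61 sets the routine grading rule: "Pretreatment symptoms/conditions to be graded at baseline and adverse events to be graded at each evaluation per CTCAE v4.0 grading". Its table marks AST increased, alkaline phosphatase increased and blood bilirubin increased both at baseline and at each evaluation. Section 10.622 adds submission of "Grade 3 and 4 AEs regardless of attribution to the study treatment or procedure" for terms not in that table.

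After treatment, patients with confirmed progression (13.2) and those who stop for intolerability, request, physician decision or intercurrent illness (13.3) go to Event Monitoring. Section 4.1 lists no laboratory tests for that phase. Patients who complete two years go to Observation (13.4), where CBC and renal profile continue but the liver panel does not.

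Other text bears on liver tests without scheduling one at End of Treatment:
- 8.1, Grade 3-4 AST, ALT or bilirubin: "Permanently discontinue (see exception below".
- 9.51: patients are to be "carefully monitored during the treatment phase and then followed appropriately".
- 9.52: contact "at least every 2 weeks until the event is resolved or determined to be irreversible", limited to ongoing agent-related serious events.
- 9.663, AST or ALT at Grade 3 or above: "Discontinue pembrolizumab. Initiate systemic steroid therapy".
- 9.673, bilirubin at Grade 3 or above: "Monitor levels until resolved to" Grade 1 or lower.
- 15.194 asks for close monitoring of liver tests as a sign of early autoimmune hepatitis.

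**The concern.** Safety is half of the primary goal (2.1), and 16.31 will report, for each type of toxicity, the proportion of patients with a severe level. A transaminase or bilirubin rise without symptoms is found only if blood is tested. The schedule brings patients back at End of Treatment, assesses adverse events and draws blood for three other panels, but leaves out the one that detects hepatic toxicity. For most routes off treatment this is also the last scheduled blood draw.

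The plan itself treats the period as relevant. Section 10.41 uses a reporting period of 30 days after the last administration, and 15.191 warns that side effects can appear up to months after stopping. What is at stake is under-ascertainment of a new hepatic event that starts after the final Day 1 panel.

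**Working it through.** **1. Marks in section 4.0, row by row**

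| Row | Pre-registration | Day 1 | End of Treatment | Observation, every 12 weeks | At progression |
|---|---|---|---|---|---|
| AE assessment | X | X | X | X | X |
| CBC | X | X | X | X | X |
| Renal profile | X | X | X | X | X |
| FT4 and TSH | X | X | X | – | – |
| Liver panel | X | X | – | – | – |

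The renal profile contains no liver analyte, so it cannot stand in for the missing panel.

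**2. Laboratory terms in 10.61 graded at each evaluation**

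- From the CBC: anemia, neutrophils, platelets, white cells = 4.
- From the liver panel: AST, alkaline phosphatase, bilirubin = 3.
- Without a scheduled test at End of Treatment: 3 / (4 + 3) = 3 of 7. Febrile neutropenia is not counted, as it is not a laboratory value alone. ALT is in the panel but not in the 10.61 list.

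**3. Is there a later scheduled panel?**

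- Confirmed progression or early stop, then Event Monitoring: none (4.1).
- Two years completed, then Observation: none in either column (4.0).
- A further Day 1 visit takes place, for example because dosing is withheld there or a confirming evaluation is done at that visit: one panel does follow the last dose.
- No further Day 1 visit: the last scheduled panel is that of the final cycle's own Day 1, within its 3-day tolerance.

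**4. Age of the last scheduled panel at End of Treatment**

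The plan gives no window for this visit. Assume it falls when the next Day 1 would have been due (7.1: 21 ± 3 days):

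21 − 3 = 18 days to 21 + 3 = 24 days.

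If the visit coincides with a Day 1 visit, the age is 0 and there is no gap. On the 18 to 24 day assumption, and counting 10.41's 30 days from the last infusion, the visit falls inside that period with 30 − 24 = 6 to 30 − 18 = 12 days left. Imiquimod is applied on weekdays through the cycle, so the period can run later still.

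**5. Size**

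One missed severe event among 10 patients changes the 16.31 proportion for that term by 1/10 = 10 percentage points. The chance of this cannot be computed. Section 15.17 lists hepatitis among toxicities below 1%, which in 10 patients gives fewer than 10 × 0.01 = 0.1 expected cases over the whole course, and only part of those would fall after the last Day 1. It also lists increased AST above 10%, but does not split this by grade. Neither figure is for the combination.

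**The case against.** The strongest reply is that section 4.0 is not the only source of liver tests. Section 8.1 holds pembrolizumab for a Grade 2 rise until Grade 0-1, with a 12-week limit. Its footnote for patients with liver metastases turns on a rise lasting at least one week. Neither can be applied without repeat tests. Section 9.673 calls for monitoring bilirubin to resolution, 15.194 is not confined to Day 1, and 10.7 refers late events to forms that are not part of the document. This stands as mitigation. It does not close the gap, because the rules in 8.1 and 9.673 start from an abnormality already seen, 10.7 concerns submission, and 15.194 fixes no time.

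Three stronger readings are tempting, and the documents do not support them.

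- **That 4.0 and 10.61 flatly contradict each other.** *Evaluation* is not defined, and sections 11 and 16.21 use it for disease evaluations. The mismatch exists only if the word covers each visit with an adverse event assessment.
- **That a Grade 3 AST or ALT found on Day 1 would be lost to the safety analysis.** That event is already detected, gradable and counted under 16.31. What lacks a schedule is documentation of its course, which is clinical follow-up of a known problem. Nor does 8.1 require discontinuation in every such case, given its liver-metastasis exception.
- **That response or the stopping rule is compromised.** Response does not use liver tests. The rule in 16.61 concerns Grade 4 events during treatment, when a panel is scheduled every cycle.

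It is also fair to say that an added panel is only as useful as the timing of a visit whose window the plan leaves open. If End of Treatment falls on the Day 1 at which the drug is stopped, a second panel adds nothing.

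**Conclusion.** The point holds as a minor gap in safety ascertainment. The liver panel is the only blood panel drawn on Day 1 of each cycle that is not repeated at End of Treatment, and the plan gives no reason. The exposure is narrow: a new, symptom-free hepatic event arising after the final Day 1 panel, in a patient with no further Day 1 visit and no for-cause test. The expected number in 10 patients is small and cannot be estimated from the documents.

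The count of 3 of 7 terms assumes that *evaluation* in 10.61 includes End of Treatment. The 18 to 24 day age assumes that the visit replaces the next Day 1. The blank cell itself depends on neither assumption.

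**What to change.** In the section 4.0 table, mark the liver-panel row at End of Treatment, with a footnote that it is not required if a Day 1 panel was obtained at the same visit.

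Marking that cell alone would leave the same question open in Observation, so also do one of the following:
- mark the panel in the two Observation columns, where CBC and renal blood is already drawn; or
- state in 10.61 that the AST, alkaline phosphatase and bilirubin terms apply through End of Treatment.

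Cost: 10 patients × 1 visit = at most about 10 panels, on blood already scheduled, so a small laboratory charge with no extra visit or procedure. Marking Observation as well would add roughly 52 / 12 ≈ 4 panels for each patient who completes that year without progression. The second option costs one sentence. A panel at End of Treatment will not detect hepatic effects that first appear later, during Event Monitoring.

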4.1 Event Monitoring/Survival Follow-up

	Event Monitoring Phase ¹				
	q. 6 months until PD	At PD	After PD q. 6 months	Death	New Primary
Event Monitoring	X	X	X	X	At each occurrence

1. If a patient is still alive 3 years after registration, no further follow-up is required.

5.0 Stratification Factors OR Grouping Factor:

None

6.0 Registration/Randomization Procedures

- 6.1 To register a patient, access the Mayo Clinic Cancer Center (MCCC) web page and enter the registration/randomization application. The registration/randomization application is available 24 hours a day, 7 days a week. Back up and/or system support contact information is available on the Web site. If unable to access the Web site, call the MCCC Registration Office at [REDACTED] between the hours of 8 a.m. and 4:30 p.m. Central Time (Monday through Friday).

The instructions for the registration/randomization application are available on the MCCC web page [REDACTED] and detail the process for completing and confirming patient registration. Prior to initiation of protocol treatment, this process must be completed in its entirety and a MCCC subject ID number must be available as noted in the instructions. It is the responsibility of the individual registering the patient to confirm the process has been successfully completed prior to release of the study agent. Patient registration via the registration/randomization application can be confirmed in any of the following ways:

- Contact the MCCC Registration Office [REDACTED] If the patient was fully registered, the MCCC Registration Office staff can access the information from the centralized database and confirm the registration.
- Refer to “Instructions for Remote Registration” in section “Finding/Displaying Information about A Registered Subject.”

- 6.2 Correlative Research.

A mandatory correlative research component is part of this study, the patient will be automatically registered onto this component (see Sections 3.19c and 17.1).

- 6.3 Documentation of IRB approval must be on file in the Registration Office before an investigator may register any patients.

In addition to submitting initial IRB approval documents, ongoing IRB approval documentation must be on file (no less than annually) at the Registration Office [REDACTED]. If the necessary documentation is not submitted in advance of attempting patient registration, the registration will not be accepted and the patient may not be enrolled in the protocol until the situation is resolved.

When the study has been permanently closed to patient enrollment, submission of annual IRB approvals to the Registration Office is no longer necessary.

- 6.4 Prior to accepting the registration, registration application will verify the following:
- IRB approval at the registering institution
 - Patient eligibility
 - Existence of a signed consent form
 - Existence of a signed authorization for use and disclosure of protected health information

- 6.5 At the time of registration, the following will be recorded:
- Patient has/has not given permission to store and use his/her sample(s) for future research of melanoma at Mayo Clinic.
 - Patient has/has not given permission to store and use his/her sample(s) for future research to learn, prevent, or treat other health problems.
- 6.6 Treatment cannot begin prior to registration and must begin ≤ 14 days after registration.
- 6.7 Pretreatment tests/procedures (see Section 4.0) must be completed within the guidelines specified on the test schedule.
- 6.8 All required baseline symptoms (see Section 10.6) must be documented and graded.
- 6.9a Treatment on this protocol must commence at Mayo Clinic Florida under the supervision of a medical oncologist.
- 6.9b Study drug is available on site.

